All subjects will be randomized to receive double-blind treatment consisting of either ALZ-801 265mg BID or matched placebo with similar appearance. Subjects will be randomized in a 1:1 ratio to either active or placebo arms. Subjects and their study partners, study personnel at the clinical sites and all Sponsor staff will remain blinded to treatment assignement till after database lock and unblinding. Double-blind treatment will be dispensed in blister packs. Details regarding the randomization stratification can be found in Section 3.1.

During the conduct of the study, the personnel who perform the unblinded safety analysis for the Data and Safety Monitoring Board (DSMB) will be shielded from the study team by a firewall and other appropriate standard operating procedures. These steps are further described and documented in the DSMB charter.

Subjects whose treatment assignment is unblinded for safety purposes will be listed and the reasons for unblinding will be documented prior to database lock and unblinding.

In the event that prescreening/baseline data were mistakenly entered into the Interactive Response Technology for randomization and stratification purposes, a listing of all such misstratifications will be provided. Using the intent-to-treat (ITT) principle, efficacy analyses for such subjects will be performed "as randomized". For the statistical models used for analyses, the "as randomized" variables corresponding to the stratification factors will be used as

For safety analyses, the correct stratification factors will be used to classify subjects in the actual stratification categories or subgroups.

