4.1 Primary Clinical Outcome

The target study sample size was 300 subjects randomized or 150 subjects per treatment group, based on ADAS-Cog 13, the primary clinical outcome. The study completed enrollment with 325 randomized subjects. The ADAS-Cog 13 is a well-validated and widely-used measure of global cognition in AD observational studies and Phase 3 drug trials. This scale evaluates multiple cognitive domains including memory, language, praxis, orientation, and executive function. To improve the sensivity of ADAS-Cog in MCI patients, two additional items were added to the original 11-item scale, including delayed word recall and digit cancellation (Mohs 1997).

Study Sample Size

Sample size determination was based on ADAS-cog results from an AD trial with tramiprosate, the active agent in ALZ-801. These efficacy data were observed in Mild AD patients (baseline MMSE =22-26) with APOE4/4 genotype who received tramiprosate 150mg BID over 78 weeks (Abushakra 2017). The tramiprosate 150mg BID dose provides plasma exposures similar to ALZ-801 at 265mg BID, the dose used in the current study.

In the 78-week tramiprosate Phase 3 study, the APOE4/4 Mild AD patients showed approximately 5.0-point difference from placebo (benefit) on ADAS-Cog. Since this Phase 3

For the primary efficacy outcome of ADAS-Cog 13, this study is powered to detect a 3.0-point difference between the active ALZ-801 treatment and the placebo in the CBL to Week 78. An increase in ADAS-Cog scores denotes cognitive worsening. It is expected that the mean baseline ADAS-Cog 13 in both groups will be 22.0 (standard deviation [SD] 6.7), which is expected to increase by 6 points in placebo (CBL: 6.0, SD 5.6), and 3 points in the active drug arm (CBL: 3.0, SD 8.1). A sample size of 125 completed subjects per arm will provide > 90% power to detect a difference of 3 points on ADAS-Cog. The drop-out rate is estimated to be approximately 17% at 78 weeks, thus a total of 300 subjects enrolled would provide approximately 250 completers (125 per arm).

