8.1.2 Hypothesis Testing

[figure not shown]
The Null Hypothesis of the study is that the CBL of ADAS-Cog 13 in ALZ-801 arm is not different from the placebo arm at 78 weeks.

The Alternate Hypothesis is that the CBL of ADAS-Cog 13 (Mohs 1997) in ALZ-801 arm is different from the placebo at 78 weeks.

The statistical testing will be two-sided and will be performed at the α =0.05 significance level. The key secondary efficacy endpoints will be compared only after the comparison of the primary endpoint has reached statistical significance. The comparisons of key secondary

endpoints will be done using a graphical approach (Bretz 2009) that strongly controls the family-wise Type 1 errors arising from multiple comparisons (Figure 2).

Figure 2 Graphical Approach Procedure for Analysis of Key Secondary Outcomes

[figure not shown]

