8.3.3 Analyses of Key Secondary and Other Secondary Endpoints

The same MMRM method applied to the primary efficacy endpoint will be used to evaluate the between-treatment difference for the key secondary endpoints and the other secondary endpoints using the FAS. The same treatment policy strategy as that applied to the primary efficacy endpoint will be used for the secondary efficacy endpoints analysis. Differences between the two treatment groups, the p-values, and the 2-sided 95% CIs will be calculated within the framework of MMRM. The model will include all terms as in the primary endpoint model except that the baseline values will be corresponding to the baseline value for each parameter. Note that only the post-baseline visits on which the endpoints are scheduled to be measured will be included in the model.

The main analysis population is the FAS. Similar sensitivity analyses as for primary endpoint will be repeated for the key secondary and other secondary endpoints. As supportive analysis, the key and other secondary endpoints will also be analyzed using the PPP, and CP. Additional sensitivity analyses using MMRM with Last Observation Carried Forward (LOCF) may be performed.

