8.3.6.1 Time to Disease Progression

Additional efficacy analyses may include time-to-event (time to first disease progression) analyses using the CDR-SB and A-IADL-IRT scores. The CDR-SB analysis will evaluate the delay in progression from MCI to Mild AD stage or worse, and from Mild AD to Moderate or Severe AD (O'Bryant 2008). The A-IADL-IRT analysis will evaluate delay in functional decline, or progression from a category of "No-Mild" to "Moderate" or worse, or from "Moderate" to "Severe" functional deficits (Dubbelman 2022a). The time-to-event analyses will also be performed based on the CDR-G and MMSE scores. The categories for time-to-progression events are defined below for CDR-SB, CDR-G, A-IADL-IRT, and MMSE scores:

- CDR-SB: CDR-SB progresses from category of MCI (SB \leq 4.0) to Mild AD or worse (SB \geq 4.5); or from Mild AD (SB = 4.5-9.0 inclusive) to Moderate AD or worse (SB \geq 9.5)
- CDR-G: CDR-G progresses from MCI (CDR-G = 0.5) to Mild AD or worse (CDR-G \geq 1.0); or from Mild AD (CDR-G = 1.0) to Moderate AD or worse (CDR-G \geq 2.0)
- A-IADL-IRT: The A-IADL-IRT scores change from category of No or Mild deficits (≥ 50) to Moderate deficits or worse (<50); or from Moderate deficits (40-49 inclusive) to Severe deficits (< 40)
- MMSE: MMSE progresses from MCI (MMSE >26) to Mild AD or worse (MMSE ≤ 26); or from Mild AD (MMSE 22-26, inclusive) to Moderate AD (MMSE ≤ 21)

Time-to-Event Analysis

The time-to-event is measured from day of randomization to day of the earliest progression event (to next category). Subjects who do not experience the event by the study's end or drop out for other reasons will be censored. A Cox proportional hazard regression analysis (Cox 1972) will incorporate the treatment group and four stratification factors (use of AChEI, age group, disease severity, and gender) as covariates to determine whether there is a difference in the time to event between the ALZ-801 and placebo arms. The resulting hazard ratios, 95%

confidence intervals, and p-values will be reported. In addition, we will estimate the distribution of delaying progression in each treatment group using the Kaplan-Meier method (Kaplan 1958). The Kaplan-Meier method will provide probability estimates for patients with progression. Kaplan-Meier curves will be presented for each treatment arm, along with medians for time to progression and 95% confidence intervals.

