8.3.6.2 Time to Emergence or Worsening of Neuropsychiatric/Behavioral Symptoms

The NPI scale will be used to evaluate the emergence or worsening of specific neuropsychiatric symptoms (NPS) of interest. Emergence of a NPS is defined as an NPI sub-item score = 0 at baseline that becomes ≥ 3 at subsequent study visit. The NPS of interest are the following:

- Cluster 1: Irritability, anxiety, depression/dysphoria
- Cluster 2: Agitation/Aggression, aberrant motor behaviours
- Cluster 3: Delusions, hallucinations

The catergories for NPS emergence or worsening are defined by NPI sub-item score (frequency × severity, Table 14):

- Baseline NPI sub-item score < 3 increases to NPI sub-item score ≥ 3 on one or more of Cluster 1 NPS
- Baseline NPI sub-item score < 3 increases to NPI sub-item score ≥ 3 on either agitation/aggression or aberrant motor behaviours of Cluster 2 NPS
- Baseline NPI sub-item score < 3 increases to NPI sub-item score ≥ 3 on either delusions or hallucinations of Cluster 3 NPS

Time-to-Event Analysis

The time-to-event is measured from day of randomization to day of earliest emergence or worsening of a NPS (NPI sub-item score) based on the above definitions. Emergence is defined as a NPS with NPI sub-item score = 0 at baseline and becomes > 0 at a subsequent study visit. Worsening is defined as a NPS with NPI sub-item score of 1 or 2 at baseline and becomes \geq 3 at a subsequent study visit. Subjects who do not experience the event by the study's end or drop out for other reasons will be censored. The same statistical analysis methods will be employed as in Section 8.3.6.1.

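### The Cox models for time to progression omit starting stage and baseline score; adding both is a minor, free gain in power, mainly for CDR-SB and probably A-IADL-IRT

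*SAP*

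**What the plan says.** SAP Section 8.3.6.1 describes time-to-first-progression analyses on four scales. Those on CDR-SB and A-IADL-IRT are optional; the next lines say that those on CDR-G and MMSE will be done as well. Progression means moving from the starting category to the next worse one:

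- CDR-SB: from 4.0 or less to 4.5 or more, or from 4.5–9.0 to 9.5 or more.
- A-IADL-IRT: from 50 or more to below 50, or from 40–49 to below 40.
- CDR-G: from 0.5 to 1 or more, or from 1 to 2 or more.
- MMSE: from above 26 to 26 or less, or from 22–26 to 21 or less.

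Both transitions on a scale feed one clock. The Cox model "will incorporate the treatment group and four stratification factors (use of AChEI, age group, disease severity, and gender) as covariates". Sections 8.3.1 and 8.3.2 show that the severity factor is MMSE at or below 26 versus above 26. No stratification by starting category is stated. By contrast, in the MMRM of Section 8.3.3 "the baseline values will be corresponding to the baseline value for each parameter". Section 8.3.6.2, on neuropsychiatric symptoms, reuses the approach: "The same statistical analysis methods will be employed as in Section 8.3.6.1". Under Section 8.1.5, p-values for endpoints outside the alpha graph are nominal.

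**The concern.** The event depends mechanically on where a subject starts. On CDR-SB a subject at 4.0 progresses after 0.5 points (4.5 − 4.0) and one at 1.0 after 3.5 (4.5 − 1.0). One at 4.5 needs 5.0 (9.5 − 4.5), yet shares a baseline hazard with the subject at 4.0. The MMSE split is only a rough stand-in for CDR-SB or A-IADL-IRT stage.

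Leaving a strong prognostic factor out of a Cox model moves the hazard ratio toward 1 and lowers power, so a real delay in progression may look like little or none. The missing information is already to hand. A baseline score is needed to assign the starting category, and the MMRM already adjusts for baseline CDR-SB, MMSE and A-IADL (in its weighted form). The SAP gives no reason for dropping it here.

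**Working it through.** **What the plan gives.** Testing: "The statistical testing will be two-sided and will be performed at the α =0.05 significance level" (SAP 8.1.2). Allocation: "Subjects will be randomized in a 1:1 ratio to either active or placebo arms" (SAP 3.3). Size: "The study completed enrollment with 325 randomized subjects" (SAP 4.1). Dropout: "The drop-out rate is estimated to be approximately 17% at 78 weeks" (SAP 4.1). CDR is rated after baseline at Weeks 26, 52 and 78, and MMSE at six visits (SAP Appendix 1). No hazard ratio, event count or power is stated for any Cox model.

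**The plan's own power figures.** These concern ADAS-Cog 13 only, and they reproduce. SD = √((8.1² + 5.6²)/2) = 6.963. SE = 6.963 × √(2/125) = 0.881. At 3.0 points, Φ(3.0/0.881 − 1.96) = 0.926; at 2.5 points, 0.810. The SAP says above 90% and about 80%.

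**Main CDR-SB simulation.** N = 325, 1:1, 17% dropout, Efron ties, 700–1,500 trials per row, Monte Carlo SE at most about 1.9 points. Placebo decline is 1.25/0.81 = 1.54 points, from the earlier tramiprosate subgroup in Protocol 2.3.1.1. Assumed, not in the documents: baseline mean and SD, SD of change, score reliability (0.8 in the rows shown), correlation of the MMSE split with the score (0.4, also 0.7), and the slowing.

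| Slowing | SD of change | Baseline mean/SD | Events | Planned model: HR, power | Plus linear baseline: power | Stage strata plus baseline: HR, power | Information ratio |
|---|---|---|---|---|---|---|---|
| 35% | 2.0 | 3.3/1.7 | 112 | 0.78, 23% | 24% | 0.75, 35% | 1.39 |
| 50% | 2.0 | 3.3/1.7 | 107 | 0.71, 41% | 40% | 0.66, 53% | 1.40 |
| 81% | 2.0 | 3.3/1.7 | 100 | 0.56, 82% | 82% | 0.51, 91% | 1.33 |
| 35% | 1.6 | 3.3/1.7 | 109 | 0.76, 30% | 30% | 0.72, 38% | 1.46 |
| 50% | 1.6 | 3.3/1.7 | 104 | 0.68, 50% | 50% | 0.62, 66% | 1.49 |
| 50% | 2.0 | 2.8/1.3 | 112 | 0.68, 52% | 52% | 0.64, 61% | 1.30 |

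Over all runs of this set the gain was about 6–17 points, or 1.25–1.6 times the information. Distance to threshold in place of strata did equally well (55% in the second row).

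**Other assumed inputs.** With 162 per arm, 50–70% starting as MCI, decline 1.6, SD of change 1.0–2.0 and 35% slowing (400 trials each), mean z and power moved as follows. The information ratio is the squared ratio of mean z.

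- −1.58 to −2.00 (32% to 54%): (2.00/1.58)² = 1.60
- −1.76 to −2.43 (45% to 65%): (2.43/1.76)² = 1.91
- −1.41 to −1.65 (29% to 39%): (1.65/1.41)² = 1.37
- −1.42 to −1.76 (32% to 41%): (1.76/1.42)² = 1.54

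Further runs at N = 325 gave 27% against 49%, 24% against 35% and 47% against 58%. Rejection under the null was about 3–6% for both models.

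**Is pooling the problem?** No. In the second row, the pooled event with stage strata and baseline has 53% power; MCI-to-Mild alone with baseline has 46%. Without baseline adjustment the figures are 41% pooled and 38% alone.

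**Why a linear baseline score is not enough.** Risk rises as the score nears 4.0, drops at 4.5, then rises again toward 9.5. One slope cannot follow that.

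**If the severity factor already equals the starting stage**, as nearly holds for MMSE, the same simulation gives 49% against 58%, ratio 1.18.

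**Unconfirmed MMSE events.** Take a subject truly stable at m, with independent normal noise (SD 1–2, assumed) and integer scores. Per visit, p = Φ((26.5 − m)/SD). Over six visits the chance of at least one score of 26 or less is 1 − (1 − p)⁶. At m = 27, p = 0.309–0.401, giving 89–95%; at m = 28, p = 0.067–0.227, giving 34–79%. If progression must be seen again at the next visit, or be first seen at the last visit, these become 39–54% and 7–27%. At m = 29 and 30 the unconfirmed rates are 4–49% and 0–22%.

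**The case against.** The strongest reply is that little is at stake. The p-values are nominal, part of the analysis is optional, no power is claimed, and the planned test holds its type I error. The confirmatory analyses of ADAS-Cog 13, A-IADL-W and CDR-SB do adjust for baseline. All of that stands, and it makes this a minor point. It does not defend leaving out information that costs nothing to use, since the hazard ratios and intervals will be reported.

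Some stronger readings are tempting but not supported:

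- *The models lose most of their power.* The loss is moderate and depends on assumed inputs. Only CDR-SB was simulated; A-IADL-IRT shares the structure, but its loss has not been sized.
- *Pooling two transitions is the error.* Pooling adds events. The weakness is the common baseline hazard.
- *All four scales suffer alike.* For CDR-G, entry requires 0.5 or 1 (Protocol 5.1), so starting stage is the whole baseline score. For MMSE, the severity factor is close to the starting category. It is not identical: the model uses as-randomized values (SAP 3.3), while the analysis baseline averages two scores (SAP 8.1.3).
- *The neuropsychiatric models need the same change.* Events in Section 8.3.6.2 are defined on clusters of two or three sub-items, so there is no single baseline sub-item score to enter.
- *MMSE progression is mostly test noise.* That follows only for subjects near the cut; subjects starting at 22–26 were not examined.

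The two hazard ratios also answer slightly different questions, since one conditions on more than the other. Power is therefore the fairer comparison.

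**Conclusion.** The point holds as an efficiency weakness, not as an error in validity. For CDR-SB the planned Cox model loses about 6–22 points of power against one with stage strata and baseline score, and the latter carries about 1.25–1.9 times the information. In the main simulation the hazard ratio is nearer 1 by about 0.03–0.06. The range rests on assumed baseline distribution, variability, reliability and slowing. The direction was the same in every scenario run. A smaller gain is expected for MMSE. A reader might infer that the trial's main conclusions are exposed; they are not, because these analyses sit outside the alpha graph.

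**What to change.** Amend SAP Section 8.3.6.1 before unblinding, keeping the pooled event and the four factors:

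- **CDR-SB and A-IADL-IRT:** stratify the baseline hazard by starting category (MCI or Mild; No-Mild or Moderate) and add the continuous baseline score of the same scale. Distance to threshold as a covariate is an acceptable alternative. Do not add a linear baseline score without the strata.
- **CDR-G:** stratify by starting category only; a baseline covariate would be constant within stratum.
- **MMSE:** add baseline MMSE and stratify by the category of the analysis baseline.
- **Section 8.3.6.2:** no change on this account.

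Optionally, add an MMSE sensitivity analysis that counts progression only if it is seen again at the next visit or first appears at the last one.

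The cost is a few lines of SAP text, one covariate and a STRATA statement, with no new data. The confirmation rule yields fewer events, which is why it belongs in a sensitivity analysis.

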8.3.6.2 Time to Emergence or Worsening of Neuropsychiatric/Behavioral Symptoms

The NPI scale will be used to evaluate the emergence or worsening of specific neuropsychiatric symptoms (NPS) of interest. Emergence of a NPS is defined as an NPI sub-item score = 0 at baseline that becomes ≥ 3 at subsequent study visit. The NPS of interest are the following:

- Cluster 1: Irritability, anxiety, depression/dysphoria
- Cluster 2: Agitation/Aggression, aberrant motor behaviours
- Cluster 3: Delusions, hallucinations

The catergories for NPS emergence or worsening are defined by NPI sub-item score (frequency × severity, Table 14):

- Baseline NPI sub-item score < 3 increases to NPI sub-item score ≥ 3 on one or more of Cluster 1 NPS
- Baseline NPI sub-item score < 3 increases to NPI sub-item score ≥ 3 on either agitation/aggression or aberrant motor behaviours of Cluster 2 NPS
- Baseline NPI sub-item score < 3 increases to NPI sub-item score ≥ 3 on either delusions or hallucinations of Cluster 3 NPS

Time-to-Event Analysis

The time-to-event is measured from day of randomization to day of earliest emergence or worsening of a NPS (NPI sub-item score) based on the above definitions. Emergence is defined as a NPS with NPI sub-item score = 0 at baseline and becomes > 0 at a subsequent study visit. Worsening is defined as a NPS with NPI sub-item score of 1 or 2 at baseline and becomes \geq 3 at a subsequent study visit. Subjects who do not experience the event by the study's end or drop out for other reasons will be censored. The same statistical analysis methods will be employed as in Section 8.3.6.1.

8.3.7 Additional Cognitive / Functional / Quality of Life Analysis

Additional composite scores that utilize sub items from cognitive, functional, and/or quality of life scales may be derived and analyzed, guided by emerging validation studies of composite scales in AD studies.

8.3.8 PK Analysis and Population PK Model

The plasma and CSF concentrations of ALZ-801, tramiprosate, and the metabolite (3-SPA) will be summarized and tabulated. Population PK model will be developed by a dedicated group of PK and modelling scientists according to a dedicated SAP for PK/PD modeling.

8.3.9 Correlation of PK levels to Efficacy, Safety Parameters, and Exploratory Biomarker Outcomes

- The correlation of PK parameters to clinical efficacy and safety parameters will be analyzed by estimating coefficients for meta regressions using all collected data points with subject as a random effect.
- The correlation of PK parameters to exploratory imaging and fluid biomarker outcomes will be analyzed using the same methods. Mediation analyses may be conducted to explore relationships between clinical outcomes and imaging or fluid biomarkers.

8.4 Exploratory Imaging and Biomarker Analyses

8.4.1 Analyses of Exploratory Imaging Biomarker Endpoints

Analysis of the volumetric MRI outcomes will be performed using the same MMRM approach described for analysis of the primary clinical endpoint. The MMRM model will include treatment, the use of concomitant AD medications (AChEI or none), age group (50 through 65 years or > 65 years), gender, disease severity based on baseline MMSE, baseline volumetric MRI value, visit, and treatment by visit interaction. The MRI magnet strength (1.5 or 3 Tesla) will also be included as a covariate in the model.

The imaging biomarker analyses will be performed on the imaging biomarker population.

8.4.2 Analyses of Exploratory Plasma Biomarker Endpoints

Serial plasma samples from screening and each subsequent visit will be stored and batched, under GLP conditions, for analyses after the end of study. Samples from multiple subjects and study sites will be batched and analyzed at a single central laboratory using validated assays, or well performing, widely accepted plasma assays.

The plasma biomarker analyses will be performed on the plasma biomarker population. The change from baseline and percent change from baseline in plasma biomarkers will be summarized by visit and treatment group. The change from baseline and percent change from baseline in each plasma biomarker will be analyzed using an MMRM model. The model will include treatment, the use of concomitant AD medications (AChEI or none), age group (50 through 65 years or > 65 years), gender, disease severity based on baseline MMSE, baseline plasma biomarker level, visit, and treatment by visit interaction in the model.

Serial CSF samples from the baseline, Week 52 and Week 78 visits will be stored and batched for analyses. Samples from multiple subjects and study sites will be analyzed in batches, at a single central laboratory, using standardized procedures and validated assays, or well performing, widely accepted CSF assays.

The CSF biomarker analyses will be performed on the CSF biomarker population. The change from baseline and percent change from baseline in CSF biomarkers will be summarized by visit and treatment group. The between groups comparisons of change from baseline and percent change from baseline in each CSF biomarker will be analyzed using an MMRM model with treatment, the use of concomitant AD medications (AChEI or none), age group (50 through 65 years or > 65 years), gender, disease severity based on baseline MMSE, baseline CSF biomarker level, visit, and treatment by visit interaction in the model.

